Study Intervention and Intervention Form: Ravulizumab and placebo are formulated as a sterile liquid solution and will be administered as IV infusions. The ravulizumab or placebo dose for each participant will be based on body weight.

[figure not shown]
Study/Treatment Duration: Initially a loading dose will be administered. Starting at Week 2 maintenance doses will then be administered every 8 weeks during the 26-week Randomized Controlled Period (RCP) for Part A and 50-week RCP for Part B. Participants will continue to receive ravulizumab during the OLE Period every 8 weeks for up to 130 weeks (Part A) or up to

74 weeks (Part B). The total study treatment duration for Part A and Part B will be approximately 3 years and 2.5 years, respectively.

Visit Frequency: The participant Screening Period covers 42 days before Study Day 1. For Part A, visits will be on Day 1, 15, 71, 127, and 183 during the RCP and on Day 183, 197, 253, 309, 365, 421, 477, 533, 589, 645, 701, 757, 813, 869, 925, 981, 1037, and 1079 during the OLE. For Part B, visits will be on Day 1, 15, 71, 127, 183, 239, 295, and 351 during the RCP and on Day 351, 365, 421, 477, 533, 589, 645, 701, 757, 813, and 869 during the OLE.

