Abbreviations: 30s CST = 30-second Chair Stand Test; ADA = antidrug antibody; AE = adverse event; CDA-IGA = Cutaneous Dermatomyositis Activity Physician's Global Assessment; CDASI = Cutaneous Dermatomyositis Disease Area and Severity Index; CSM = core set measures; D = day; DM-DSQ = Dermatomyositis Disease Symptoms Questionnaire; ECG = electrocardiogram; eCRF = electronic case report form; EOS = end of study; EQ-5D-5L = European Quality of Life Health 5-item questionnaire dimensions 5 level; ET = Early Termination; FACIT = Functional Assessment of Chronic Illness Therapy; HAQ = Health Assessment Questionnaire; IMACS-TIS = International Myositis Assessment and Clinical Studies-Total Improvement Score; MDAAT = Myositis Disease Activity Assessment Tool; MMT-8 = Manual Muscle Testing subset of 8 muscles; OLE = Open-Label Extension; PD = pharmacodynamic(s); PK = pharmacokinetic(s); PROMIS = Participant-reported Outcomes Measurement Information System; SF-36 = Short Form Health Survey (36 questions version; UV = Unscheduled Visit; W = week(s); WOCBP = women of childbearing potential

Table 4: Schedule of Activities: Open-Label Extension Period for Part A (Phase 2) – Week 108 – Week 156

| Period | | | Open-L | abel Exte | nsion Per | iod | | UV | Notes |
|--|-----------|--------|--------|-----------|-----------|-------|---------------|----|---|
| Visit | 17 | 18 | 19 | 20 | 21 | 22 | 23/ ET/EOS | | OLE Period begins at the start of dosing on Day 183 Participants who discontinue/withdraw from the study should complete the ET Visit 8 weeks after the participant's last dose of study |
| Days | D757 | D813 | D869 | D925 | D981 | D1037 | D1079 | | intervention. In addition, a follow-up phone call 21 weeks (± 1 week) |
| Weeks | W108 | W116 | W124 | W132 | W140 | W148 | W156 | | after the participant's last dose of study intervention will be performed to collect information on concomitant medications, non-pharmacologic |
| Window (day) | ± 3 | ± 3 | ± 7 | ± 7 | ± 7 | ± 7 | ± 7 | | therapies and procedures, and AEs (see Section 7.2 for more details). |
| Weight | X | X | X | X | X | X | X | | |
| Vital signs | X | X | X | X | X | X | X | X | On dosing days, vital signs will be taken before study intervention administration and after the participant has been resting for at least 5 minutes (see Section 8.2.4). |
| Physical Examination | | | | | | | | X | |

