| To evaluate the long-term effect of ravulizumab treatment in participants with DM based on improvement in components of the IMACS | TIS at Week 156 (Part A) or Week 124 (Part B) Change from baseline in MMT-8 at Week 156 (Part A) or Week 124 (Part B) Change from baseline in physician global activity assessment at Week 156 (Part A) or Week 124 (Part B) Change from baseline in extra-muscular disease activity based on MDAAT at Week 156 (Part A) or Week 124 (Part B) Change from baseline in HAQ at Week 156 (Part A) or Week 124 (Part B) |

Table 9: Mapping Objectives to Endpoints/Estimands for Open-Label Extension (Part A and Part B)

| Objectives | Endpoints/Estimands |
|---|--|
| To evaluate the long-term effect of ravulizumab on overall health-related quality of life (HR-QoL) and participant-centered and participant-reported outcomes in DM | Change from baseline in EQ-5D-5L at Week 156 (Part A) or Week 124 (Part B) Change from baseline in PROMIS-29 v2.1 domains at Week 156 (Part A) or Week 124 (Part B) |
| | • Change from baseline in SF-36 at Week 156 (Part A) or Week 124 (Part B) |
| | Change from baseline of DM symptoms captured in DM-DSQ at Week 156 (Part A) or Week 124 (Part B) |
| | Change from baseline of Patient Global Assessment of Disease Activity (last question in the DM-DSQ) at Week 156 (Part A) or Week 124 (Part B) |
| To characterize the long-term safety of ravulizumab in participants with DM | Incidence of TEAEs, TESAEs, and TEAEs leading to study intervention discontinuation |
| To characterize the long-term PK/PD and immunogenicity of ravulizumab in adult participants with DM | Serum ravulizumab concentration at Week 156 (Part A) or Week 124 (Part B) |
| | Change in serum free and total C5 concentrations at Week 156 (Part A) or Week 124 (Part B) |
| | Incidence and titer of ADAs through Week 156 (Part A) or Week 124 (Part B) |
| To evaluate complement, inflammatory, autoimmune and other soluble biomarkers in adult participants with DM | Change from baseline (only in subjects positive at baseline) in specific autoantibody (eg, anti-MDA5, anti-NXP2/MJ, and anti-synthetase/Jo-1, anti-TIF-1) titers over the course of the study |
| | Change from baseline in plasma complement activation (eg, sC5b-9, etc) at Week 156 (Part A) or Week 124 (Part B) |
| | Change from baseline in serum inflammatory markers (eg, IL6, etc) and other soluble markers (eg, KL6, etc) over the course of the study |

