Table 9: Mapping Objectives to Endpoints/Estimands for Open-Label Extension (Part A and Part B)

| Objectives | Endpoints/Estimands |
|--|--|
| To assess the long-term efficacy of ravulizumab in the treatment of DM based on other efficacy endpoints | Change from baseline using scale to measure pruritus (5D-itch scale) at Week 156 (Part A) or Week 124 (Part B) |
| | Change from baseline in CDASI Activity Score at Week 156 (Part A) or Week 124 (Part B) |
| | CDA-IGA response (almost clear or clear) at Week 156 (Part A) or Week 124 (Part B) |
| | Change from baseline in handheld dynamometry performance at Week 156 (Part A) or Week 124 (Part B) |
| | Change from baseline in 30-second Chair Stand Test (30s CST) at Week 156 (Part A) or Week 124 (Part B) |
| | Change from baseline in FACIT-Fatigue score at Week 156 (Part A) or Week 124 (Part B) |
| To evaluate the long-term use of DM treatment in participants with DM concurrently receiving ravulizumab | Percentage of participants steroid-free or minimal maintenance dose of 5 mg (prednisone equivalent) or less at the end of the OLE Period |
| | Cumulative steroid dose from baseline |

Abbreviations: ADA = antidrug antibody; anti-MDA5 = antimelanoma differentiation-associated protein 5; anti-NXP2/MJ = antinuclear matrix protein; anti-TIF-1 = anti-transcription intermediary factor 1; C5 = complement component 5; CDA-IGA = Cutaneous Dermatomyositis Activity Physician's Global Assessment; CDASI = Cutaneous Dermatomyositis Disease Area and Severity Index; DM = dermatomyositis; DM-DSQ = dermatomyositis disease symptoms questionnaire; EQ-5D-5L = European Quality of Life Health 5-item questionnaire dimensions 5 level; FACIT = Functional Assessment of Chronic Illness Therapy; HAQ = Health Assessment Questionnaire; IMACS = International Myositis Assessment and Clinical Studies; IL6 = interleukin 6; MDAAT = Myositis Disease Activity Assessment Tool; MMT-8 = manual muscle testing subset of 8 muscles; OLE = Open-Label Extension; PD = pharmacodynamic(s); PK = pharmacokinetic(s); PROMIS = Patient-Reported Outcomes Measurement Information System; sC5b-9 = soluble terminal complement complex; SF-36 = Short Form Health Survey (36 questions version); TEAE = treatment-emergent adverse event; TESAE = treatment-emergent serious adverse event; TIS = Total Improvement Score; Primary Estimand(s)

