4.1.2. Part B (Phase 3 Portion)

There will be 3 periods in Part B of this study: Screening Period, Randomized Controlled Period, and OLE Period. Approximately 114 eligible participants will be stratified by cutaneous manifestations (Cutaneous Dermatomyositis Disease Area and Severity Index [CDASI] Activity Score ≤ 14 and > 14) and randomized 2:1 either to ravulizumab IV infusion or placebo IV infusion (Section 6.3) within each stratum.

For each participant, the Randomized Controlled Period ends and the OLE Period begins at Week 50 (see Section 6.1.1.2 for details). During the OLE Period, participants in the ravulizumab group will continue to receive ravulizumab, and participants in the placebo group will switch to receive ravulizumab. Participants will receive ravulizumab until ravulizumab is registered or approved (in accordance with country-specific regulations) or for up to 74 weeks (approximately 1.5 years), whichever occurs first.

Randomized Controlled Period

All participants randomized into the study are expected to complete the Randomized Controlled Period and will be followed until the end of the Randomized Controlled Period.

Participants who discontinue study intervention will complete the Randomized Controlled Period (see Section 7.1). Participants that require acute therapy with standard DM treatment (see Section 6.5.3) due to protocol defined Clinical Worsening (see Section 4.1.3) and complete all remaining visits of the Randomized Controlled Period will be permitted to enter OLE Period.

Participants who discontinue/withdraw from the study will not be permitted to enter the OLE Period (see Section 7.2). Participants who will not enter the OLE Period will not receive an infusion at Week 50.

OLE Period

All participants completing the OLE Period will have an EOS Visit at Week 124 and a follow-up phone call 21 weeks (± 1 week) after the participant's last dose of study intervention to collect information on concomitant medications, non-pharmacologic therapies and procedures, and AEs.

Participants who discontinue study intervention are encouraged to complete the visits and assessments of the OLE Period (see Section 7.1).

Adjustments of 'protocol allowed' DM medications (Section 6.5.1) will be permitted throughout the OLE Period (Section 6.5.1).

Participants who discontinue/withdraw from the study will complete an ET Visit and a follow-up phone call (see Section 7.2).

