6.1.1.1. Part A

For each participant in Part A, the entire duration is up to 156 weeks, consisting of a Randomized Controlled Period (26 weeks), and an OLE Period (up to 130 weeks, last scheduled dosing at OLE Week 148).

Randomized Controlled Period

Randomized Controlled Period is a double-blind, randomized, placebo-controlled period. Eligible participants will be randomized 2:1 to receive blinded doses of ravulizumab or placebo starting on Day 1 and ending after assessments on Week 26.

- Participants in the ravulizumab group will receive a blinded loading dose of ravulizumab (10 mg/mL formulation) via IV infusion on Day 1, followed by a blinded maintenance dose at Week 2, Week 10, and Week 18 (Table 12).
- Participants in the placebo group will receive a blinded placebo via IV infusion on Day 1, followed by a blinded placebo at Week 2, Week 10, and Week 18.
- Participants who discontinue study intervention will be followed for key efficacy (Section 8.1) and safety assessments (Section 8.2) until the end of the Randomized Controlled Period, withdrawal of consent, or lost to follow-up, whichever is earlier.

Participants who will not enter the OLE Period will complete the assessments for Week 26 but will not receive an infusion at Week 26.

Open-Label Extension Period

The Randomized Controlled Period will end after all predose assessments have been completed at the Week 26 visit. The OLE Period will begin when participants, that elect to continue treatment, receive the Week 26 study intervention infusion. To maintain the treatment randomization blind of the Randomized Controlled Period, participants in both the placebo group and the ravulizumab group will receive blinded doses of ravulizumab as follows:

- Participants in the placebo group will switch to receive a blinded loading dose of ravulizumab (10 mg/mL formulation) at Week 26 (Table 12).
- Participants in the ravulizumab group will receive a blinded ravulizumab dose (10 mg/mL formulation) of 900 mg at Week 26. The 900 mg dose at Week 26 is chosen to maintain complete C5 inhibition over the 2-week period until the next scheduled maintenance dose.

Starting at Week 28, all participants will receive open-label ravulizumab maintenance doses (100 mg/mL formulation) q8w until the last scheduled dose at Week 148 (Table 12).

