9.3. Populations for Analyses

The analysis sets are defined in Table 17. Unless otherwise specified, the same definitions will be used for the statistical analyses of Part A and Part B where applicable.

Table 17: Study ALXN1210-DM-310 Analysis Populations

| Population | Description |
|------------------------|---|
| Randomized Set | All randomized participants grouped by randomized treatment group (for reporting disposition, demographics, baseline characteristics and efficacy). |
| PK Analysis Set (PKAS) | All participants who receive at least 1 dose of study intervention and have at least 1 post-dose PK sample |
| PD Analysis Set (PDAS) | All participants who receive at least 1 dose of study intervention and who have evaluable free or total C5 data |

| Population | Description | |
|---|---|--|
| Per Protocol Set (PPS) (applicable for Part B only) | All randomized participants without any major protocol deviations ^a that could impact the interpretation of efficacy. The PPS will be used for supplemental analyses of the primary and secondary efficacy endpoints. | |
| Safety Set (SS) | All participants who receive at least 1 dose of study intervention. Participants will be analyzed according to the study intervention they actually received. The SS will be used for the analysis of safety data. | |
| OLE Set | All randomized participants who received at least 1 dose of ravulizumab starting from Week 26 (Part A and Part B) onward. | |
| Immunogenicity Analysis Set (IAS) | All participants who receive at least 1 dose of study intervention and have at least one reportable result in the ADA assay. Participants will be analyzed according to the study intervention they actually received | |

Table 17: Study ALXN1210-DM-310 Analysis Populations

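### Protocol Amendment 3.0 leaves three OLE inconsistencies: seven Part A Week 156 endpoints with no assessment after Week 100, a Part B OLE Set that opens at Week 26 although the OLE starts at Week 50, and a Week 156 visit dated at Week 154

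*Protocol*

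**What the plan says.** **OLE endpoints.** Protocol Section 3, Table 9 gives most OLE endpoints one late timepoint for each part of the study. Fatigue is an example: "Change from baseline in FACIT-Fatigue score at Week 156 (Part A) or Week 124 (Part B"). PROMIS-29, the 5D-itch scale, handheld dynamometry, the 30-second chair stand test and plasma complement activation (sC5b-9) are dated in the same way, and the entry for skin response reads "CDA-IGA response (almost clear or clear) at Week 156 (Part A) or Week 124 (Part B"). The whole of Table 9 sits under an exploratory heading.

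**Part A schedule.** Section 1.3 splits the Part A OLE into Table 3 (Weeks 26 to 100) and Table 4, titled "Schedule of Activities: Open-Label Extension Period for Part A (Phase 2) – Week 108 – Week 156".

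**OLE Set.** Section 9.3, Table 17 defines it as "All randomized participants who received at least 1 dose of ravulizumab starting from Week 26 (Part A and Part B) onward". For Part B, Section 4.1.2 states that "the Randomized Controlled Period ends and the OLE Period begins at Week 50".

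**Final Part A visit.** Section 6.1.1.1 says "the entire duration is up to 156 weeks", and Table 4 labels the last visit Week 156. The same column gives Day 1079, and the synopsis visit list ends "813, 869, 925, 981, 1037, and 1079 during the OLE".

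**The concern.** An endpoint needs a scheduled measurement at its timepoint. If Table 4 is followed, the seven Part A endpoints will have no Week 156 values, and an assessment not made at a visit cannot be recovered later.

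The OLE Set should contain people treated in the OLE. Under the Table 17 wording, a Part B ravulizumab participant belongs to the set through a blinded dose given during the Randomized Controlled Period (RCP). A placebo participant, as planned, first receives ravulizumab at Week 50 and so belongs only by entering the OLE. Membership would then depend on the randomised arm, and the ravulizumab denominators could include people with no OLE exposure.

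A day and a week label that disagree give Part A sites two target dates for the last assessment.

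**Working it through.** **1. Durations.** Part A: 26 + 130 = 156 weeks. Part B: 50 + 74 = 124 weeks. Both agree with the stated totals.

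**2. Table 9 against the schedules.** Table 9 has 20 endpoints tied to Week 156 (Part A) or Week 124 (Part B). Thirteen have their input in Table 4 at the final visit: TIS, MMT-8, physician global, extramuscular activity, HAQ, EQ-5D-5L, SF-36, the two DM-DSQ endpoints, CDASI, ravulizumab concentration, C5 and ADA. The other 20 − 13 = 7 compare as follows.

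| Endpoint | Last collection in Table 3 | Table 4, any column | Table 5 (Part B), Week 124 |
|---|---|---|---|
| PROMIS-29 | Week 100 | none | yes |
| 5D-itch | Week 100 | none | yes |
| CDA-IGA | Week 100 | none | yes |
| Handheld dynamometry | Week 100 | none | yes |
| 30-second chair stand | Week 100 | none | yes |
| FACIT-Fatigue | Week 100 | none | yes |
| sC5b-9 (biomarker blood) | Week 100 | none | yes |

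The gap is 156 − 100 = 56 weeks. The early-termination/end-of-study and unscheduled-visit columns of Table 4 do not supply these measures either. Part B has none missing. Rows lost in the PDF reading are an unlikely cause: the gaps fall at several separate places in Table 4, between rows that were read intact. Autoantibody titres and inflammatory markers also have no sample after Week 100, but they are defined over the course of the study and are not counted here.

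**3. Part B OLE Set.** The Part B dosing days in the RCP (Table 13) are 1, 15, 71, 127, 183, 239 and 295. With week = (day − 1)/7, those from Week 26 onward are:

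- Day 183: 182/7 = Week 26
- Day 239: 238/7 = Week 34
- Day 295: 294/7 = Week 42

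The set therefore opens 50 − 26 = 24 weeks before the OLE, and any one of three blinded doses is enough for a ravulizumab participant to qualify. Section 4.1.5 treats those who complete Week 50 without a dose as discontinued, and Section 6.5.3 bars from the OLE those given acute therapy for reasons other than confirmed worsening. Ravulizumab participants in either group would still be in the OLE Set if dosed at or after Week 26. The ceiling is the planned ravulizumab arm, 76; for placebo it is 0.

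**4. Final Part A visit.** The other OLE visits follow day = 7 × week + 1, for example:

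- Week 26: 183
- Week 100: 701
- Week 124: 869
- Week 148: 1037

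For Week 156 the rule gives 7 × 156 + 1 = 1093. Day 1079 is (1079 − 1)/7 = Week 154. The difference is 1093 − 1079 = 14 days. With the ±7-day window the two targets cover Days 1072–1086 and 1086–1100, which share only Day 1086.

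**The case against.** The strongest reply is that little depends on this. All seven endpoints are exploratory, and no primary or key secondary analysis, alpha or power figure is involved. Long-term data on all seven exist at Week 100, 74 weeks into the Part A OLE; what is lost is the further 56 weeks. Table 4 also moves EQ-5D-5L and SF-36 to alternate visits, so the schedule may have been thinned on purpose after Week 100, in which case only the Table 9 label is wrong. The OLE section of the Part A SAP (Section 4.5) names TIS, TIS response and CDASI, all of which remain scheduled to Week 156.

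On the OLE Set, 76 is a ceiling that would require no ravulizumab participant to enter the OLE. The planning dropout rate of about 20% would give 0.20 × 76 = 15.2, roughly 15; those last dosed before Week 26 would not count, and completers who decline the OLE would add to it at an unstated rate. Someone with no OLE visits cannot shift observed means at Weeks 52 to 124, so the effect falls on set size and percentage denominators. A Part B SAP could define the set differently.

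These points limit the consequence and are accepted as such. They do not resolve the contradictions. If the thinning was intended, Table 9 must change; if not, Table 4 must. No supplied document corrects the Part B OLE Set: the OLE Set in Section 3 of the supplied SAP starts at Week 26, which is right for Part A only. Consistent use of Day 1079 in the synopsis and Table 4 does not make it Week 156.

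**Conclusion.** The concern holds on all three counts. As written, 7 of 20 Part A endpoints dated Week 156 have no scheduled measurement there. The Part B OLE Set opens 24 weeks early and admits RCP-only participants from one arm only, up to a ceiling of 76 against 0. The final Part A visit has two target dates 14 days apart.

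This is an internal inconsistency that should be corrected; it does not threaten the primary or key secondary analyses. The first count assumes that the schedule tables are complete as published. The effect of the second on reported summaries assumes that the Part B SAP carries over the Table 17 wording.

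**What to change.** - **Table 9:** for the seven endpoints, change the Part A timepoint to Week 100, where all are already collected. Alternatively, add the seven assessments, including the biomarker sample, to the Visit 23 column of Table 4.
- **Table 17:** define the OLE Set by a ravulizumab dose given in the OLE Period, from Week 26 in Part A and from Week 50 in Part B. Use the same definition in the Part B SAP.
- **Synopsis and Table 4:** reconcile Day 1079 with Week 156, so that the day, the week label and the visit window agree throughout, including the PK/PD and ADA notes that cite Day 1079.

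The cost is table edits in a protocol amendment. Re-dating to Week 100 adds no procedures; keeping Week 156 adds seven assessments at one visit.

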3.1. Primary Estimand(s)

3.1.1. Primary Estimand for Part A

The five attributes for the primary estimand are described below:

- Treatment: Ravulizumab or placebo with or without the use of stable allowed concomitant DM treatments
- Population: adult DM participants who have an inadequate response or are intolerant to at least 1 DM treatment
- Variable: TIS40 response at Week 26

- Intercurrent Events:
 - o Discontinued study intervention due to death, AE, or lack of efficacy during the Randomized Controlled Period.
 - Received acute therapy with standard DM treatment or prohibited medications (Section 6.5.2 and Section 6.5.3).
 - O Data handling strategy: Participants will be considered non-responders for TIS40 after experiencing these intercurrent events (composite strategy) regardless of the availability of actual TIS40 responses. All available TIS40 data will be used for participants without these intercurrent events.
- Population-level summary: Difference in the percentage of TIS40 response between ravulizumab and placebo arms

The remaining missing data handling for TIS40 is described in Section 9.4.1.2.2.

